#### 14.2.11 DAILY DIARY

Data from the daily diary and its analysis is described in Section 14.2.7.

#### 14.2.12 TEAR MEDIATORS

Analyses of tear mediators will be conducted as ad-hoc analyses. The anticipated ad-hoc analyses of tear mediators are as follows.

Percent change in tear mediators from Visit 2 (Day 1) to Visit 6 (Day 57) will be summarized using continuous descriptive statistics by treatment group. Pairwise two-sample t-tests will be employed to compare treatment and placebo means. Comparisons between treatment groups and between all active groups and placebo will also be conducted. The differences in means, two-sided 95% confidence intervals (CIs) for the difference in means and p-values will be reported. Wilcoxon rank sum tests will also be conducted.

Association between percent change in tear mediators and select efficacy endpoints will be summarized by treatment group and for the active treatment groups combined using Pearson and Spearman correlation coefficients, with 95% confidence intervals constructed using Fisher's Z-transformation. Efficacy endpoints and changes from baseline may also be summarized using continuous descriptive statistics by tertiles of percent change in tear mediators for each treatment group and for the active treatment groups combined. Pairwise comparisons between tertile groups will also be conducted. The differences in means, two-sided 95% confidence intervals (CIs) for the difference in means and p-values will be reported. Wilcoxon rank sum tests will also be conducted.

Analyses will be performed on the ITT population with observed data only.

### 15. Safety Analyses

All safety analyses will be conducted using the Safety population.

#### 15.1 Adverse Events

An AE is defined as any untoward medical occurrence associated with the use of an investigational product (IP) in humans, whether or not considered IP-related. An AE can be any unfavorable and unintended sign (eg, an abnormal laboratory finding), symptom, or disease temporally associated with the use of an IP, without any judgment about causality. An AE can arise from any use of the IP (eg, off-label use, use in combination with another drug or medical device) and from any route of administration, formulation, or dose, including an overdose. An AE can arise from any delivery, implantation, or use of a medical device, including medical device failure, subject characteristics that may impact medical device performance (eg, anatomical limitations), and therapeutic parameters (eg, energy applied, sizing, dose release) associated with medical device. All AEs will be coded using MedDRA Version 20.1.

Treatment-emergent adverse events (TEAEs) are defined as any adverse event that occurs or worsens after the first dose of study treatment. AEs recorded in the eCRF which began prior to treatment will not be included in the summary tables but will be included in the AE data listings.

An overall summary will be presented that includes the number of AEs, TEAEs, serious AEs (SAE), and serious TEAEs (TE-SAE). The summary will also include the number and percentage of subjects withdrawn due to an AE, the number and percentage of subjects with an AE resulting in death, and the number and percentage of subjects who experienced at least one AE, TEAE, SAE and TE-SAE, by treatment group and for all subjects. This summary will include breakdowns of AEs further categorized as ocular or non-ocular. The summary will also include the number and percentage of resolved ocular AEs, and the mean number of days until AE resolution for resolved ocular AEs.

Additional summaries of TEAEs will be provided showing the number and percentage of subjects who experienced at least one TEAE. These summaries will be presented by SOC and PT. Non-ocular TEAEs will be summarized using discrete summary statistics and presented by treatment group at the subject and event level by SOC and PT. Ocular TEAEs will be similarly summarized at the subject and event level as well as for study and fellow eyes separately. If a subject reports the same PT multiple times within the same SOC, that PT will only be reported once within that SOC. As with the PT, if a subject reports multiple conditions within the same SOC, that SOC will only be reported once. In the summary, SOC will be listed in order of descending frequency for all subjects; PTs will be listed in order of descending frequency for all subjects within each SOC. The occurrence of non-ocular and ocular TEAEs will also be tabulated by SOC, PT, and maximal severity, as well as by study day of onset (prior to Day 9, Day 9 to Day 29, After Day 29).

Separate summaries will be provided for the following categories of AEs:

- Ocular TEAEs
- Non-ocular TEAEs
- Treatment-related ocular TEAEs
- Treatment-related non-ocular TEAEs
- SAEs

Severity of an adverse event is defined as a qualitative assessment of the degree of intensity of an adverse event as determined by the investigator or reported to him/her by the patient/subject. The assessment of severity is made irrespective of relationship to study drug or seriousness of the event and should be evaluated according to the following scale:

- *Mild*: Event is noticeable to the subject, but is easily tolerated and does not interfere with the subject's daily activities.

- *Moderate*: Event is bothersome, possibly requiring additional therapy, and may interfere with the subject's daily activities.
- *Severe*: Event is intolerable, necessitates additional therapy or alteration of therapy, and interferes with the subject's daily activities.

Summaries of TEAEs by maximal severity will be presented for ocular AEs and non-ocular AEs separately. The number of subjects with any TEAEs (along with percentages) will be tabulated by SOC and PT within each SOC by treatment group. To count the number of subjects with any TEAEs, if a subject has multiple TEAEs coded to the same PT within the same SOC, the subject will be counted once under the maximal severity.

The relationship of each adverse event to the investigational product should be determined by the investigator (in a blinded manner) using these explanations:

- *Definite*: Relationship exists when the AE follows a reasonable sequence from the time of IP administration, follows a known response pattern of the drug class, is confirmed by improvement on stopping the IP and no other reasonable cause exists.
- *Probable*: Relationship exists when the AE follows a reasonable sequence from the time of IP administration, follows a known response pattern of the drug class, is confirmed by improvement on stopping the IP and the suspect IP is the most likely of all causes.
- *Possible*: Relationship exists when the AE follows a reasonable sequence from the time of administration, but could also have been produced by the subject's clinical state or by other drugs administered to the subject.
- *Not Related*: Concurrent illness, concurrent medication, or other known cause is clearly responsible for the AE, the administration of the IP and the occurrence of the AE are not reasonably related in time, OR exposure to IP has not occurred.
- *Unclassified*: When the causal relationship is not assessable for whatever reason due to insufficient evidence, conflicting data or poor documentation.

All possible, probable, and definite TEAEs are considered as treatment-related TEAEs.

All AEs will be presented in a subject listing that classifies each AE as ocular or non-ocular and indicates whether it is a TEAE. Separate listings will be produced for AEs leading to study discontinuation, AEs leading to death and SAEs.

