descriptively (n, mean, standard deviation, median, min and max) by visit and treatment group, and analyzed with two-sample t-tests comparing each of the active treatment groups to placebo. All visit-based data will be analyzed at each visit and change from baseline. Change scores from pre- to post-CAE® will be calculated as Post-CAE® score – Pre-CAE® score. A Wilcoxon rank sum test and an ANCOVA model adjusting for baseline and site will also be assessed where appropriate. No imputation will be performed for secondary efficacy variables.

Fluorescein staining by region and total, Lissamine green staining by region, TFBUT, conjunctival redness, unanesthetized Schirmer's test, Drop comfort assessment, OSDI, ocular discomfort and dry eye symptoms, ocular discomfort during CAE®, pre- to post-CAE® changes, and changes from baseline in these measures will be analyzed by visit using two-sample t-tests and Wilcoxon rank sum tests, as appropriate.

The worst symptom for each subject will be identified as the symptom with the highest average score during the run-in period (Days -14 to -1) as recorded in the subject diary. The worst symptom and each individual symptom will be analyzed per day using a two-sample t-test. Additionally, the average score for the worst symptom and each individual symptom will also be analyzed separately using a Wilcoxon rank sum test.

Safety Variables

Adverse events will be coded using the MedDRA dictionary. Frequencies and percentages of subjects with treatment-emergent adverse events (TEAEs), serious TEAEs, and TEAEs causing premature discontinuation will be provided by treatment group. An AE is treatment emergent if it occurs or worsens after the first dose of study treatment. Furthermore, frequencies will be given of subjects with TEAEs by system organ class, by system organ class and preferred term, by system organ class, preferred term and maximal severity, by system organ class, preferred term and strongest relationship, and by system organ class, preferred term, maximal severity, and strongest relationship. Separate analyses will be performed for ocular specific and all AEs (including systemic).

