8.3.1 Visit 1: Day -14 ± 1 – CAE® Screening

All subjects will undergo the following screening assessments:

Pre-CAE®

- Informed Consent/HIPAA Prior to any changes in a subject's medical treatment and/or invasive procedures (e.g., controlled adverse environment), the study will be discussed with each subject and subjects wishing to participate must give written informed consent and sign a HIPAA form.
- Demographic Data and Medical/Medication/Ocular History Collect and record all demographic data, medical history, any medications and any underlying condition(s). Significant non-ocular medical history only within the past year and medications within the past 30 days will be captured. Record any medications the subject is taking, as well as those the subject may have taken but discontinued within 30 days prior to screening.
- Review of Inclusion/Exclusion Criteria
- Urine Pregnancy Test (for females of childbearing potential) Women of childbearing potential must have a negative urine pregnancy test to continue in the study.
- Ora Calibra® Ocular Discomfort Scale

- Ora Calibra® Ocular Discomfort and 4-Symptom Questionnaire Ocular Discomfort Score
- Ocular discomfort using a visual analog scale (VAS)
- OSDI®
- BCVA Utilizing an ETDRS Chart Subjects must have a score of [REDACTED] logMAR or better (Snellen equivalent score of [REDACTED]) in each eye at Visit 1.
- Slit Lamp Biomicroscopy A slit lamp exam will be performed at the beginning of the visit and again Post-CAE® to exclude subjects with disallowed ocular conditions.
- Conjunctival Redness Score An objective measure used to score redness on the Ora Calibra® Conjunctival Redness Scale for Dry Eye. Half point increments (0.5) may be used.
- TFBUT
- Corneal and Conjunctival Staining (fluorescein) as assessed by the Ora Calibra® Corneal and Conjunctival Staining Scale for Grading of Fluorescein Staining
- Corneal and Conjunctival Staining (lissamine green) as assessed by the Ora Calibra® Corneal and Conjunctival Staining Scale for Grading of Lissamine Green Staining
- Monitoring and Query AEs Report any AEs that occur after signing the ICF.

Screening Challenge (CAE® #1)

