9 ADVERSE EVENTS

An AE is defined as any untoward medical occurrence associated with the use of an investigational product (IP) in humans, whether or not considered IP-related. An AE can be any unfavorable and unintended sign (eg, an abnormal laboratory finding), symptom, or disease temporally associated with the use of an IP, without any judgment about causality. An AE can arise from any use of the IP (eg, off-label use, use in combination with another drug or medical device) and from any route of administration, formulation, or dose, including an overdose. An AE can arise from any delivery, implantation, or use of a medical device, including medical device failure, subject characteristics that may impact medical device performance (eg, anatomical limitations), and therapeutic parameters (eg, energy applied, sizing, dose release) associated with medical device.

All AEs spontaneously reported by the subject and/or in response to an open question from study personnel or revealed by observation, physical examination or other diagnostic procedures will be recorded in the source document and on the appropriate pages of the CRF. Any clinically relevant deterioration in clinical finding is considered an AE and must be recorded. When possible, signs and symptoms indicating a common underlying pathology should be noted as 1 comprehensive event.

Documentation regarding the AE should be made as to the nature, date of onset, end date, severity, relationship to IP, action(s) taken, seriousness, and outcome of any sign or symptom observed by the physician or reported by the subject upon indirect questioning.

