10.4.7 Safety Variables

Adverse events will be coded using the MedDRA dictionary. Frequencies and percentages of subjects with treatment-emergent adverse events (TEAEs), serious TEAEs, and TEAEs causing premature discontinuation will be provided by treatment group. An AE is treatment emergent if it 1) occurs after the first dose of randomized study treatment or 2) if it is present prior to receipt of randomized study treatment but worsens in severity or increases in frequency after the first dose of randomized study treatment. Furthermore, frequencies will be given of subjects with TEAEs by system organ class and preferred term; by system organ class, preferred term and maximal severity; by system organ class, preferred term for treatment-related AEs; by system organ class and preferred term for SAEs; and by system organ class, preferred term, and day of onset. Separate analyses will be performed for ocular specific and all AEs (including systemic).

Other safety endpoints including visual acuity, slit lamp biomicroscopy, dilated fundoscopy, and intraocular pressure, will be summarized by treatment group and visit using descriptive statistics. Changes or shifts from baseline will also be summarized where appropriate. For assessments performed by eye, study eye and fellow eye will be summarized separately. In addition, shifts from baseline to worst on-treatment value for ocular safety assessments will be summarized.

Immunogenicity will be summarized using discrete summary statistics. Counts and proportions will be presented by visit and treatment group. Exact 95% Clopper-Pearson confidence intervals will be presented. Treatment groups will be compared using Fisher's Exact Test, and exact 95% confidence intervals for the pairwise proportion differences will be constructed.

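### SAP 15.1 counts an AE that worsens after first dose as treatment-emergent, then bars every AE that began before treatment from the summary tables

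*SAP*

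**What the plan says.** SAP 15.1 gives the definition first: "Treatment-emergent adverse events (TEAEs) are defined as any adverse event that occurs or worsens after the first dose of study treatment". The sentence after it states that "AEs recorded in the eCRF which began prior to treatment will not be included in the summary tables"; those events go to the data listings. The next paragraph plans an overall summary of "the number of AEs, TEAEs, serious AEs (SAE), and serious TEAEs (TE-SAE", that is, all events and treatment-emergent events as separate counts. Later in the same section, the AE listing "classifies each AE as ocular or non-ocular and indicates whether it is a TEAE".

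The table list in SAP 19 follows that separation. Tables 14.3.1.2 and 14.3.1.3 cover all AEs, 14.3.1.4 and 14.3.1.5 cover TEAEs, and 14.3.1.8 covers all SAEs.

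The protocol defines a TEAE twice. The synopsis says "An AE is treatment emergent if it occurs or worsens after the first dose of study treatment". Section 10.4.7 is fuller: besides new events it includes one already present that "worsens in severity or increases in frequency after the first dose of randomized study treatment".

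SAP 1 says that the SAP's analysis methods replace those in the protocol. SAP 17 declares no changes from the protocol's analyses.

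**The concern.** The definition and the exclusion cannot both be followed for an event that starts before treatment and worsens after it. Such events can occur here. Protocol 8.3.1 instructs sites to "Report any AEs that occur after signing the ICF", and subjects then pass through two screening CAE exposures and about 14 days of open-label placebo before the first randomized dose. An ocular event that starts in that period and worsens on study drug belongs in the comparison with placebo. A programmer who applies the exclusion sentence as written would leave it out of the tabulated comparison while flagging it as a TEAE in the listing.

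The sentence also refers to the summary tables without limiting itself to the TEAE tables. It therefore reaches outputs meant to show all AEs and all SAEs, and removes the pre-treatment events that distinguish them from the TEAE outputs.

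**Working it through.** The point is textual, and the plan gives no figure to reproduce.

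**1. The two sentences of SAP 15.1, case by case**

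| Onset | Course after first dose | TEAE by the definition? | In summary tables by the exclusion? | Consistent for TEAE tables? |
|---|---|---|---|---|
| After first dose | any | Yes | Yes | Yes |
| Before treatment | does not worsen | No | No | Yes |
| Before treatment | worsens | Yes | No | **No** |

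For the TEAE tables the conflict is confined to the third row.

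**2. The all-event counts**

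Let *a* be events that began before treatment and did not worsen, *b* those that began before and worsened, and *c* those that began after first dose. The plan intends AE = *a* + *b* + *c* and TEAE = *b* + *c*.

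- Exclusion read literally: the tables hold *c* only, so AE = TEAE = *c*.
- Exclusion read charitably, as removing only non-worsened events from the summary tables: AE = TEAE = *b* + *c*.

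Under both readings the two counts coincide, and SAE coincides with serious TEAE in the same way. The overall summary plans all four as distinct quantities, so the charitable reading repairs the TEAE tables but not the others.

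**3. Tables under the literal rule (SAP 19)**

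- TEAE tables: 14.3.1.4 to 14.3.1.7 (4) and 14.3.1.9 to 14.3.1.12 (4), giving 8.
- Overall summary 14.3.1.1 (1), all-AE tables 14.3.1.2 and 14.3.1.3 (2), SAE table 14.3.1.8 (1), giving 4.
- Total: 8 + 4 = 12, which is every AE table in the list.

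**4. Whether other text settles the conflict**

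- Protocol 10.4.7 includes worsened pre-existing events, but SAP 1 gives the SAP precedence on analysis methods. SAP 17 declares no changes, so the exclusion is not presented as a deliberate departure.
- Protocol 9 treats a clinically relevant deterioration in a finding as an AE to be recorded, and asks for "the nature, date of onset, end date, severity, relationship to IP, action(s) taken, seriousness, and outcome". It does not say that a worsened AE gets a new record with its own onset date. If every worsening were a new event, the worsening limb of the TEAE definition would be redundant.
- Protocol 9.5 asks for a new form when an SAE changes. That is a reporting step and sets no onset rule.

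**5. Size**

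The documents give no rate of run-in AEs and no rate of worsening, so the expected number of affected subjects cannot be computed. With the planned 50 subjects per arm:

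- Effect of one omitted subject with no other TEAE in that count: 1/50 = 2.0 percentage points.
- Effect of one omitted subject who has another TEAE in that count: 0.
- If 1, 2 or 3 subjects in an arm were omitted with no other TEAE in the count (an assumption, for illustration only): 2, 4 or 6 points.

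**The case against.** The strongest reply is that the exclusion sentence directly follows the TEAE definition and reads naturally as its complement: events that are not treatment-emergent go to the listings. The rest of SAP 15.1 supports that intent, since it tabulates subjects with at least one TEAE without an onset restriction, flags TEAE status in the listing and separates AE from TEAE counts. This is a plausible guess at intent, but it is not written. It would also leave the all-AE and SAE counts in conflict with the sentence, as step 2 of the working shows.

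A second reply is that a worsened finding recorded under protocol 9 might carry a post-dose onset date, so that the two sentences agree. That may narrow the problem, but it depends on eCRF instructions that are not in the documents, and it may not reach purely subjective symptoms.

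Third, the difference between study treatment and randomized study treatment is small in practice. Protocol 10.4.1 and SAP 9.3 place the start of study treatment usually at Visit 2, and SAP 13.2 counts exposure from Visit 2. This stands. The remaining substantive difference between the two protocol definitions is the limb on increased frequency.

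Fourth, the consequence is limited. The AE outputs are descriptive, the trial is a Phase 2 study that SAP 9.5 calls primarily exploratory, the events concerned arise only in randomized subjects over a short run-in, and all of them stay in the listing. This also stands. It bears on the size of the effect and does not remove the contradiction.

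**Conclusion.** The concern holds. As written, SAP 15.1 classes a worsened pre-treatment AE as a TEAE and excludes it from the tables that count TEAEs, contrary to protocol 10.4.7. It also makes the AE and SAE counts identical to the TEAE and serious TEAE counts that are planned beside them. All 12 AE tables fall under the literal rule, although in the eight TEAE tables only worsened pre-treatment events are affected.

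The wording conflict is certain; its numerical effect is unknown. The per-subject figure of 2.0 points assumes 50 subjects in the arm and no other TEAE in that count, and the 2 to 6 point range rests on an assumed number of subjects. No efficacy conclusion depends on it, and a check of listing against tables would recover the omitted events. It should be corrected before unmasking, so that the counting rule is not chosen with treatment codes known.

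**What to change.** Replace the exclusion sentence in SAP 15.1 with wording such as:

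> *AEs that began before the first dose of randomized study treatment and did not worsen afterwards are excluded from the TEAE tables only; they remain in the all-AE and SAE tables and in the listings.*

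Reconcile the two protocol definitions, and use the one in section 10.4.7, tied to randomized treatment, in SAP 15.1. Apply its increased-frequency limb only where the eCRF captures frequency: the AE attributes named in protocol 9 do not include it, and the eCRF specification is not among the documents.

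The cost is one SAP sentence, one programming flag and alignment of the synopsis wording. TEAE counts may rise slightly. Applying the frequency limb would need a data source that protocol 9 does not name.

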9.5 TYPE AND DURATION OF THE FOLLOW-UP OF SUBJECTS AFTER ADVERSE EVENTS

The investigator will follow unresolved AEs to resolution until the subject is lost to follow-up or until the AE is otherwise classified. Resolution means the subject has returned to baseline state of health or the Investigator does not expect any further improvement or worsening of the AE. If the patient is lost to follow-up, the Investigator should make 3 reasonable attempts to contact the patient via telephone, post, or certified mail. All follow-up will be documented in the subject's source document. Non-serious AEs identified on the last scheduled contact must be recorded on the AE eCRF with the status noted.

If the Investigator becomes aware of any new information regarding an existing SAE (i.e., resolution, change in condition, or new treatment), a new SAE/Unanticipated Report Form must be completed and faxed to Ora within 24 hours of the site's awareness of the new information. The original SAE form is not to be altered. The report should describe whether the event has resolved or continues and how the event was treated.

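### Ocular AE duration is summarised only as a mean among resolved events, which reads low and understates differences in duration between arms

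*SAP*

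**What the plan says.** SAP section 15.1 puts two items on ocular event outcome into the overall AE summary. The first is a count: "The summary will also include the number and percentage of resolved ocular AEs". The second is the duration figure: "the mean number of days until AE resolution for resolved ocular AEs". No other duration statistic is planned for ocular events, and the SAP does not say how ongoing events are handled. The subject counts in this summary are shown "by treatment group and for all subjects", and SAP section 9.4 makes presentation by treatment group the default, so both items can be expected by arm. Section 15.1 also plans a listing: "All AEs will be presented in a subject listing that classifies each AE as ocular or non-ocular".

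The protocol supplies the dates. Section 9 states: "Documentation regarding the AE should be made as to the nature, date of onset, end date, severity". Section 9.5 sets the follow-up rule: "The investigator will follow unresolved AEs to resolution until the subject is lost to follow-up or until the AE is otherwise classified". It counts an event as resolved when the subject is back to baseline health, or when "the Investigator does not expect any further improvement or worsening of the AE". It then adds: "Non-serious AEs identified on the last scheduled contact must be recorded on the AE eCRF with the status noted". The last scheduled visit is Visit 6 (Day 57 ± 3), after 56 days of treatment.

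**The concern.** Whether an event enters the mean depends on how long it lasted. For a given onset day, a longer event is more likely to be open at last contact and so to be excluded. The remaining events are a sample tilted towards short durations, and the tilt is stronger in an arm whose events last longer. The figure is then low in every arm and lowest relative to the truth in the arm where duration matters most.

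Open events are realistic here. No visit is scheduled after Visit 6, SAP section 15.1 has an onset category for events after Day 29, and Protocol section 9.5 foresees non-serious events recorded with a status at the last contact. At stake is a reader's impression of how long ocular events last on each concentration compared with placebo. The efficacy analyses, the significance level and the power are not touched.

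**Working it through.** The documents state no AE duration, onset pattern or number of ocular events, so there is no plan figure to reproduce. What follows is an illustration over a range of follow-up.

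**Input from the documents**
- Treatment period T = 56 days (Protocol section 8.8).

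**Assumptions**
- Onset is uniform over the T days.
- Durations are exponential with true mean m of 14 or 28 days.
- Observation stops F days after the end of treatment, with F = 0, 14 or 30. The documents give no value for F.

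**Formulas.** The time available to observe an event is uniform between F and F + T. Write a = exp(−F/m) and b = exp(−(F + T)/m).
- Proportion resolved: P = 1 − (m/T)(a − b)
- Contribution of resolved events: K = m − (m/T)[(F + 2m)a − (F + T + 2m)b]
- Mean among resolved events: K/P

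**Worked case, F = 0**
- m = 14: P = 1 − 0.25(1 − e⁻⁴) = 0.755. K = 14 − 0.25(28 − 84e⁻⁴) = 7.385. K/P = 9.79 days.
- m = 28: P = 1 − 0.5(1 − e⁻²) = 0.568. K = 28 − 0.5(56 − 112e⁻²) = 7.579. K/P = 13.35 days.

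| Follow-up after Day 56 | True mean 14 d reads (resolved) | True mean 28 d reads (resolved) | Apparent ratio (true 2.0) |
|---|---|---|---|
| None | 9.8 d (75%) | 13.4 d (57%) | 1.36 |
| 14 days | 11.3 d (91%) | 16.2 d (74%) | 1.43 |
| 30 days | 12.7 d (97%) | 19.4 d (85%) | 1.53 |
| All events to resolution | 14 d (100%) | 28 d (100%) | 2.00 |

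Ratios use unrounded means. From rounded means the first is 13.4/9.8 = 1.37. A simulation of 2,000,000 events per setting agrees to within 0.02 days (9.78, 13.35, 12.74 and 19.46 days for the first and third rows; the last rounds to 19.5, giving 19.5/12.7 = 1.54).

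**Does the percentage resolved repair the mean?** It warns the reader but does not give the duration. With 14 days of extra follow-up, a true mean of 28 days gives 74% resolved. With none, a true mean of 14 days gives 75%. Nearly the same percentage goes with durations that differ twofold.

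**Where the percentage does the work.** Suppose no events in one arm and 20% in the other never resolve, the rest last 5 days on average, and F = 0. The resolved-only mean is 4.5 days in both arms, but the percentage resolved is 91.1% against 72.8%. The mean misses this contrast and the planned percentage shows it.

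**Does allowing for censoring help?** In the simulation with F = 0, total observed time divided by the number of resolved events returns 14.0 and 28.0 days. The true medians are m·ln 2 = 9.7 and 19.4 days, again 2.0-fold. A Kaplan-Meier curve estimates these if censoring is unrelated to duration.

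**The case against.** A reader might infer that the plan hides differences between arms. The documents do not support that. The percentage resolved stands in the same sentence, it can be expected by arm, and in the illustration without follow-up it moves with the mean (75% against 57%), so the worse arm is visible. Every AE is also listed by subject.

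A reader might also infer that the longest events are always the ones dropped. That is too strong. Some open events simply began late, Protocol section 9.5 directs that unresolved events be followed, and its definition of resolution lets some persistent but stable events count as resolved.

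The no-follow-up case is thus one end of a range, with no bias at the other end. It is also fair that duration is not among the safety variables in SAP section 3.3 and that nothing is tested on it.

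All of this limits the point without removing it. Follow-up under section 9.5 can end at loss to follow-up or when the event is otherwise classified, so some events may stay open at database lock. The percentage resolved mixes onset timing, length of follow-up and duration. A listing does not correct a summary by arm. The broad definition of resolution, on which SAP section 15.1 is silent, is a further reason to define the row.

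**Conclusion.** The point holds as a minor one. The only planned ocular duration figure conditions on resolution, so it is biased low and understates differences in duration between arms whenever longer events are left open. Under uniform onset and exponential durations, a true 2.0-fold difference (14 against 28 days) appears as about 1.4-fold with no follow-up after exit, about 1.5-fold with 30 more days, and undistorted with complete follow-up. The direction of the bias follows from the definition of the statistic. Its actual size cannot be computed from the documents. The consequence is confined to one descriptive row of the AE summary.

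**What to change.** In SAP section 15.1, keep the number and percentage of resolved ocular events. Beside them, add by arm the Kaplan-Meier median time to resolution for ocular TEAEs, with events still open censored at last contact. State two definitions:
- whether events are counted per subject or per eye, and how repeated events in one subject are treated;
- whether an event with no further change expected, as in Protocol section 9.5, counts as resolved.

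Onset date, end date and outcome are already collected. The cost is one added row, two sentences of definition and a last-contact date for each open event. There are two downsides. The median may not be reached if few events resolve, which should then be reported as such. Events within a subject are not independent, so the row should stay descriptive, without a test between arms.
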